### **3.8.1 Binary analyses of mRS**

A binary analysis of the mRS at 3 months will be performed by dichotomising the mRS as either ‘poor’ (scores 3-6) or ‘favourable’ (scores 0-2) outcomes. This analysis will be conducted using an unadjusted random-effect logistic regression that is similar to Model 1 (see Section 3.7.1), but this time with a binomial outcome and a logit link function. The effect of the intervention will be presented as the OR of a poor outcome with associated 95% CI. We will also apply the covariate adjustments described in Section 3.7.2; however, no subgroup or imputed analysis will be performed on this outcome. A similar analysis will be performed on mortality alone (mRS of 6 vs 0-5) and on dependency alone (mRS 3-5 vs 0-2). For dependency alone, the analysis will be restricted to subjects who are alive at 90 days (mRS 0-5).

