### 3.1 Statistical principles

#### 3.1.1 Level of statistical significance

The study includes two formal interim analysis after approximately one third and two thirds of patients have completed their 90-day follow-up, using the Haybittle-Peto stopping rule (3 standard-deviations) for efficacy. To account for these two interim analyses, the significance threshold will be set at 4.82% for the final analysis. In case the trial is stopped early, the significance threshold will be adjusted accordingly, to account for the amount of 'alpha' spent.

Final analysis of the primary outcome, including sensitivity analyses, will all be conducted using a two-sided significance level of 4.82%.

For the 7 secondary clinical outcomes ([1] death or dependency at 7 days, and the following at 90 days: [2] death or major disability, [3] death, [4] disability, [5] HRQoL, [6] Duration of hospitalisation and [7] residence ), the family-wise error rate will be controlled by applying a sequential Holm-Sidak correction. Briefly, the approach consists of ordering all p values from smallest to largest, and then comparing them to an adjusted level of significance calculated as  $1-(1-0.05)^{1/C}$ , where C indicates the number of comparisons that remain. In the case of seven 7 secondary outcomes, the smallest p value would be compared to  $1-(1-0.05)^{1/7}$ , the second p value to  $1-(1-0.05)^{1/6}$ , and so on, with the last one being compared to  $1-(1-0.05)$  (i.e. 0.05). The sequential testing procedure stops as soon as a p value fails to reach the corrected significance level. This will apply only to the primary analysis of the secondary outcomes (i.e. not to the adjusted models). For HRQoL, it will only apply to the analysis of the overall score. For ICH outcomes, the Heidelberg Bleeding Classification (HBC) criteria will be considered the primary measure with other definitions considered supportive. No multiplicity adjustment will be applied to the two imaging outcomes (infarct and oedema size) which are considered intermediary mechanistic outcomes.

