## 3.2 Data sets analysed

**Intention-to-treat (ITT) population:** The ITT population will consist of all patients randomised regardless of whether they received the allocated intervention. This will be used as the basis to assess both efficacy and safety.

**Efficacy analysis set:** The main analysis set will consist of all patients in the ITT population with a non-missing primary outcome (i.e. those who are known to have died or with mRS cores at 90 days). In case of missing data leading to exclusion from the ITT population, sensitivity analyses will be performed (see Section 3.7.4).

**Per-protocol (PP) analysis set:** The PP set will consist of patients from the efficacy analysis who did not have a relevant protocol violation, defined as any of: age <18 years; final diagnosis not AIS; SBP <140 mmHg (inclusion criteria BP level); EVT undertaken >24 hours; EVT did not achieve reperfusion (eTICI score <2b); and failure to obtain a blind assessment of the 90-day outcome. The per-protocol set will be applied as a sensitivity analysis.

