#### **3.7.4 Treatment of missing data**

The proportion of data missing for the primary outcome (mRS at 90 days) will be described while blinded to the intervention. In case of non-negligible amounts of missing data (>5%), we will use controlled multiple imputations to assess under what conditions the results change, and how plausible these conditions are, using the approach described by Cro et al.

We will first run an imputation model under the missing at random (MAR) assumption. This MAR imputation model will use fully conditional specification (FCS) and will include the following variables: mRS at 90 days, the NIHSS at 7 days (or hospital discharge, if sooner), a variable indicating the intervention, and all key socio-demographic, clinical, and medical baseline variables. The mRS at 7 or 90 days and NIHSS at 7 days will be imputed using an ordinal logistic model. Other variables will be imputed using either linear regression (for continuous/ordinal variables) or a discriminant function method (for nominal variables). One hundred sets of imputed data will be created and analysed using the model described in Section 3.7.1. Estimates of the treatment effect ( $e^{\theta}$  in Model 1) and its standard errors will be combined to obtain a pooled common OR and 95%CI.

Using the same 100 sets of imputed data as our base, we will then assume different mRS levels for subjects who had missing mRS data at 90 days and had their mRS value imputed. We will assume that those with a missing mRS were more likely to have a poorer outcome than those with a non-missing mRS; we will therefore add 1 to their imputed mRS score (with a maximum score of 6 for those with no vital status available or a maximum score of 5 for those known to be alive). We will then analyse the 100 modified-imputed dataset and combine the results using the same strategy as for the base set of imputed data. As an additional sensitivity analysis, we will impute all missing mRS score at 90 days with the worst possible score (i.e. a score of 6 for those with unknown vital status and a score of 5 for those known to be alive but with a missing mRS).

While this assumption is unlikely to hold in most cases, it is plausible that some subjects may have become uncontactable due to death or serious deterioration after hospital discharge.

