## **3.8 Analysis of secondary outcomes**

All secondary outcome analyses described in this section will be performed in the efficacy (primary) and PP (sensitivity) analyses sets as defined in Section 3.2.

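### Death, a formally tested secondary outcome, is taken from the mRS rather than from vital status, so patients known to be alive without a 90-day mRS are dropped from the death comparison

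*SAP*

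**What the plan says.** Four parts of the SAP together determine who enters the death comparison.

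- **Status of the outcome.** SAP 3.1.1 lists death as item [3] of seven secondary clinical outcomes for which "the family-wise error rate will be controlled by applying a sequential Holm-Sidak correction".
- **Coding.** SAP 3.8.1, after describing the analysis of mRS 3-6 versus 0-2, states: "A similar analysis will be performed on mortality alone (mRS of 6 vs 0-5". Table 13 labels the row as mRS 6.
- **Analysis set.** SAP 3.8 states: "All secondary outcome analyses described in this section will be performed in the efficacy (primary) and PP (sensitivity) analyses sets". SAP 3.2 limits the efficacy set to patients with a non-missing primary outcome, explained as "those who are known to have died or with mRS cores at 90 days".
- **Missing scores.** SAP 3.7.4 foresees a group that is alive but unscored. In one sensitivity analysis of the primary outcome it assigns "a score of 5 for those known to be alive but with a missing mRS". For the binary mRS analysis, SAP 3.8.1 says that "no subgroup or imputed analysis will be performed on this outcome", and Table 13 has no imputed row for death.

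Neither document defines a death endpoint based on vital status or time to death. The Protocol (6.10.5, Death) does collect the date and time of each death.

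**The concern.** A patient known to have died enters the death analysis without any mRS interview. A patient known to have survived enters only if the interview was completed. Inclusion therefore depends on the outcome. For a known survivor without an mRS nothing is missing as far as death is concerned: the non-event was observed, and the coding discards it.

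The group is plausible. SAP Table 17 counts refusal of the 90-day assessment separately from loss to follow-up. The trial is open label (SAP 2.1), so patients know their allocation, and the design cannot rule out refusal related to arm. If refusal or missed interviews among survivors differed between arms, the odds ratio for a formally tested outcome would move for a reason unrelated to mortality.

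**Working it through.** **Inputs.** Control mortality of 15.3% (mRS 6), 5% loss to follow-up and a total of 2257 come from SAP 2.5. Allocation of 1:1 comes from Protocol 6.1. The share of the 5% loss that is known to be alive is not given, so it is varied below as an assumption.

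**The plan's own figure.** The SAP states no figure for death, only the total for the ordinal analysis. Whitehead's formula, N = 12(z₁₋α/₂ + z₁₋β)² / [ln(OR)² (1 − Σp̄³)], with OR 0.77, α = 0.0482 and 90% power gives 1913 evaluable patients. Then 1913 / 0.95 (loss) / 0.95² (drop-in/drop-out) = 2231, which is 1.2% below 2257. The total is thus close to reproduced. It matters here only as the source of about 1128 patients per arm.

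**Death proportion.** Let *m* be the fraction of an arm that is known to be alive without an mRS. Among patients with known vital status, the reported proportion is 0.153 / (1 − m).

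| m | Reported death proportion |
|---|---|
| 0 (vital-status coding) | 15.3% |
| 1% | 0.153/0.99 = 15.5% |
| 2.5% (half of the loss) | 0.153/0.975 = 15.7% |
| 5% (all of the loss) | 0.153/0.95 = 16.1% |

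**Odds ratio when missingness is balanced.** If the same fraction *r* of survivors is unscored in both arms, each arm's survivor count is multiplied by (1 − r). The factor cancels, and the crude OR is unchanged.

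**Odds ratio when missingness differs.** Assume equal true mortality of 15.3% and fractions *a* and *b* of the two arms known alive but unscored. The reported OR, second arm versus first, is

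[0.153/(0.847 − b)] / [0.153/(0.847 − a)] = (0.847 − a)/(0.847 − b).

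- a = 3%, b = 7%: 0.817/0.777 = 1.05.
- a = 2%, b = 8%: 0.827/0.767 = 1.08.

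Both cases average 5%, so they assign the whole planned loss to known survivors.

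**Against sampling error.** With 1128 per arm there are 0.153 × 1128 ≈ 173 deaths per arm. For 3% versus 7%, the analysed survivors number 0.97 × 1128 − 173 ≈ 921 and 0.93 × 1128 − 173 ≈ 876. The standard error of the log OR is √(1/173 + 1/921 + 1/173 + 1/876) ≈ 0.117, and it is about the same in the other case. The shifts are ln(1.05)/0.117 ≈ 0.43 and ln(1.08)/0.117 ≈ 0.64 standard errors. A nominal two-sided 5% test would then reject a true null about 7% and 10% of the time. With vital-status coding the OR stays at 1.00 in every case.

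These are crude odds ratios without the site effect and covariates of the planned model.

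**The case against.** **Small size, extreme assumptions.** The documents give only a total loss of 5%. The odds ratios of 1.05 and 1.08 need all of that loss to be known survivors and a 2.3-fold or 4-fold imbalance between arms. This stands, and the figures should be read as assumed extremes.

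**Few such patients.** The 90-day visit can be by telephone or face to face with a blinded assessor (Protocol 6.10.5). SAP Table 18 also accepts information from a caregiver, the patient's doctor or another source. Most contacts that establish survival could therefore also give an mRS. This reduces the number but does not remove it: refusals are foreseen, and patients themselves are not blinded.

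**Deaths appear elsewhere.** SAE forms are required for all deaths, and SAP Tables 15 and 16 show deaths by arm. Neither table supplies a tested comparison based on vital status.

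**Convention and additivity.** mRS 6 means dead, and one common denominator keeps death, disability and their composite additive. That is a real convenience, but it does not justify discarding an observed non-event. The sentence ruling out imputation is written for the poor-outcome analysis and reaches mortality only through the word similar. Counting a known survivor as alive is not imputation in any case. It is the entry rule of the efficacy set that excludes these patients.

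**Two stronger readings.** A reader might infer that no death is ever missing under this rule, so that it must overstate true mortality. The documents do not support that. SAP 3.2 admits only known deaths, and SAP 3.7.4 accepts that some patients may be uncontactable because they died. For example, assume that half of the 5% loss is known alive and half has unknown status, and that a fraction *q* of the unknown group died. The reported proportion is (0.153 − 0.025q)/0.95, which falls below 15.3% once q exceeds 0.00765/0.025 ≈ 31%. A reader might also take death to be the trial's main safety outcome. SAP 2.4.2 gives that role to symptomatic haemorrhage by the Heidelberg criteria.

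**Conclusion.** The point holds as a cheap improvement with a small expected effect. SAP 3.2, 3.8 and 3.8.1, read together, drop known survivors without an mRS from a formally tested death comparison and keep every known death. Among patients with known vital status, the death proportion rises by 0.4 percentage points if half of the planned loss is known survivors, and by at most 0.8 points if all of it is.

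The comparison between arms is distorted only if this missingness differs by arm. Nothing in the documents shows that it does. Even the assumed extremes are well under one standard error, and the Holm-Sidak thresholds, which start at 1 − 0.95^(1/7) = 0.0073, can be stricter than the nominal 5% used above. The direction of error against true mortality is not fixed, because deaths among patients with unknown vital status are missing under the present rule and under the proposed one.

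**What to change.** In SAP 3.8.1 and Table 13, define death at 90 days from vital status in all randomised patients:

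- death on or before day 90: event;
- confirmed alive at day 90 or later by any contact: no event, with or without an mRS;
- day-90 vital status unknown: missing, with the number reported by arm.

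Because the 90-day visit has a window of ±7 days (Protocol 6.10.5), add that an mRS of 0-5 scored within the window counts as alive, as it does now. An earlier contact, such as at discharge, should not count as survival to day 90.

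The cost is SAP wording. Date of death is already collected, SAP 3.7.4 already separates known-alive from unknown status, and SAP 3.8.6 already uses last-known-alive information. The sponsor should check that the date of the last contact confirming survival is held in the database. The one drawback is that the death denominator will differ slightly from that of the mRS outcomes, which a footnote to Table 13 should explain. The mRS analyses themselves do not change.

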### **3.8.2 ICH outcomes**

ICH is defined according to 5 definitions (see Section 2.4.2) but the primary measure will be with the Heidelberg criteria. These will be reported as the number and proportion of subjects experiencing an event. The effect of the intervention will be estimated using the same approach as in the binary analysis of mRS (see Section 3.8.1). We will apply the covariate adjustments described in Section 3.7.2; however, no subgroup or imputed analysis will be performed on this outcome.

### **3.8.3 NIHSS score at 7 days**

The NIHSS score at 7 days will be categorised into 7 levels (<5, 5-9, 10-14, 15-19, 20-24, ≥25, and death), and analysed using the same method as the mRS score described in Section 3.7.1. As a sensitivity analysis, the NIHSS score will also be analysed as a continuous variable using an unadjusted hierachal linear regression model that is similar to Model 1, but assuming a normal distribution and an identity link function. The effect of the intervention will be presented as the mean difference and associated 95%CI. The covariate adjustments described in Section 3.7.2 will also be applied; however, no subgroup or imputed analysis will be performed on this outcome.

### **3.8.4 Imaging endpoints**

Infarct and oedema size will be analysed using linear mixed models with the same fixed and random effects as the main outcome analysis. Given that baseline measurements may not be available for all patients, we will use a constrained longitudinal data analysis (cLDA) model with both the baseline value and the follow-up value included as outcomes. The cLDA model constraints the mean baseline values to be equal between the two arms, which is a plausible assumption in a randomised trial. This approach has the advantage that any patient with at least one measurement (baseline or follow-up) can be included in the analysis instead of discarding patients with a missing baseline measurement. The effect of the intervention will be estimated as the mean difference and 95%CI at the follow-up time.

### **3.8.5 HRQoL**

Each of the 5 EQ-5D dimensions will be analysed via ordinal logistic regression using the same model as for the primary analysis of mRS at 90 days (Section 3.7.1). The visual analogous scale (score of 0 to 100) will be analysed using the same approach but with linear regression (i.e. assuming a normal distribution and an identity link function). We do not plan adjusted or subgroup analyses. Further analysis of EQ-5D will be undertaken as part of an economic evaluation, which is outside the scope of this SAP.

### **3.8.6 Duration of hospitalisation**

Duration of hospitalisation will be analysed as the time to discharge censored at 90 days or when the subject was last known to be alive and in hospital, whichever is earlier. It will be summarised using cumulative incidence functions treating mortality as a competing risk. Medians and quartiles of time to discharge will be obtained from the cumulative incidence functions. The effect of the intervention will be estimated as the hazard ratio (intervention divided by control) and its 95%CI obtained from a Cox model of the cause-specific hazard, which estimates the risk of discharge in subjects who are still alive and have not yet been discharged. Fixed effects will include the intervention and the stratification variables (time from onset and baseline NIHSS). Site will be adjusted for using a shared-parameter frailty Cox model with a random site effect. No adjusted or subgroup analyses are planned.

### **3.8.7 Residence**

The patient's place of residence at 90 days will be analysed as a binary outcome using the same approach as for the binary analysis of the mRS at 90 days (Section 3.8.1). For the purpose of the model, residence will be defined as follows:

- (1) home: own home (independent or with assistance) or family member's home
- (2) institution: hospital, care facility or other

No adjusted or subgroup analyses are planned.

### **3.8.8 Serious adverse events (SAEs)**

SAEs will be summarised as the number of events as well as the number and proportion of patients experiencing at least one SAE event. This will be done overall and by category of event according to Medical Dictionary for Regulatory Activities (MeDRA) system organ classes and preferred terms. The overall proportion of patients with SAEs in the intervention and control arms will be compared using logistic regression as in the binary analysis of mRS (see Section 3.8.1). Primary and underlying causes of deaths will be summarised by treatment arm with no formal test.

## **3.9 Analysis of substudies**

The main purpose of the substudies is to define recruitment, safety and adherence to the protocol, to inform the feasibility of future confirmatory studies.

Description of the baseline characteristics will be presented by treatment group. Discrete variables will be summarised by frequencies and percentages. Percentages will be calculated according to the number of patients for whom data are available. Continuous variables will be summarised using mean and SD, and median and IQR. Baseline measures will include all socio-demographic, clinical and medical information, collected at baseline.

The main outcomes will be recurrent ischaemic stroke, ICH, death, and any SAE over 12 months. These data will be reported as the number and proportion of subjects experiencing an event. The effect of the intervention will be estimated using the same approach as in the binary analysis of mRS (see Section 3.8.1). We will apply the covariate adjustments described in Section 3.7.2; however, no subgroup or imputed analysis will be performed on this outcome.

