11.2 Duration of dual antiplatelet therapy (DAPT)

11.2.1 Aims

Compared with a standard duration of DAPT (3 months), a short duration (6 weeks) of DAPT is at least as effective ('not inferior') in reducing the risk of recurrent stroke over 12 months, in AIS patients with LAA who undertook MT (i.e. corresponding null hypothesis is that short duration of treatment is inferior than standard duration on this outcome).

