11.2.3 Study design

This substudy – **Duration of DAPT** - is a pilot study imbedded in the main ENCHANTED2 study. Consent will be obtained prior to MT procedure, but randomisation will be undertaken post-MT at the same time of the main study, according to separate eligibility criteria. Randomised allocation (1:1 ratio) of intervention will be done via the same randomisation system as the main study, according to minimized method stratified by site and randomisation of BP intervention. The patients will be either allocated to short duration (6 weeks) or standard duration (3 months) of DAPT within 48 hours after AIS onset, and to be maintained on antiplatelet monotherapy (aspirin or clopidogrel) thereafter.

Study population

All patients randomised in the main trial, who have a final diagnosis of LAA-related AIS will be considered for enrolment in this sub-study. *In comparison to all other randomised patients, patients included in this substudy are followed up for 12 months.*

Inclusion and exclusion criteria

To be eligible for inclusion for this substudy, patients who has been enrolled into the main study **ARE** to still satisfy all of the following criteria:

- Final diagnosis of LAA confirmed by imaging during MT procedure

- b) Provision of written informed consent (or via an appropriate proxy, according to local requirements)

Patients will **NOT** be eligible if there is one or more of the following:

- c) Definite contraindication to both aspirin and clopidogrel

Treatment allocation

Short duration of DAPT

The patients will receive oral (including nasogastric if required) DAPT (aspirin 100 mg and clopidogrel 75 mg per day) for **6 weeks** within 48 hours after stroke onset if no PH confirmed by imaging after MT. If the patient is intolerance with aspirin or clopidogrel, cilostazol / dipyridamole can be used as a substitute.

Standard duration of DAPT

The patients will receive oral (including nasogastric if required) DAPT (aspirin 100 mg and clopidogrel 75 mg per day) for **3 months** within 48 hours after stroke onset if no PH confirmed by imaging after MT. If the patient is intolerance with aspirin or clopidogrel, cilostazol / dipyridamole can be used as a substitute.

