11.2.4 Study outcomes

Primary outcome: new stroke event (ischaemic or haemorrhagic) over 12 months

Secondary outcomes are:

- a) Major adverse cardiovascular events (MACE), defined as a combination of recurrent AIS, myocardial infarction (MI) and all-cause mortality over 3 and 12 months
- b) Recurrent AIS over 3 months and 12 months
- c) Any ICH reported by investigators or after central adjudication of relevant brain imaging over 3 months and 12 months
- d) sICH, in which ICH is related to substantial neurological deterioration or death according to various definitions over 3 months and 12 months
- e) Death or disability by shift analysis of scores on the mRS at 3 months and 12 months
- f) Separately on death and disability at 3 months and 12 months
- g) Neurological deterioration ≥ 4 points decline in NIHSS score over 7 days after randomisation
- h) Length of hospital stay
- i) HRQoL by the EuroQoL at 3 months and 12 months

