11.2.6 Sample size

In this and the other substudy, the aim is to recruit as many patients to inform the sample size estimates for the main study. Our preliminary sample size calculation to provide a reliable assessment of the treatment effect is outline below.

Ma et al. reported the proportion of post-stenting events of recurrent AIS and ICH over 12 months was 5.8% among patients with symptomatic intracranial atherosclerotic stenosis in China.⁶⁹ Considering on a broader inclusion of hospital sites and severe study population, the event rates were set up as 10%. As recommended by the United States Food and Drug Administration (FDA), the clinical margin representing the largest acceptable inferiority of the test to control is set at 50% of the margin of the excess risk. In this study, a relative non-inferiority margin of 40% (i.e. risk ratio 1.4) was used to provide assurance that short duration of DAPT retains at least 60% of the effects of reducing stroke recurrence risk compared with standard duration. A sample size of 2366 provides 90% power (1-sided $\alpha = 0.025$) to reject a non-inferiority margin of 1.4 from an expected event rate of 10% in the standard duration arm and assuming no true difference between the two durations.

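### SAP 3.9 gives the DAPT substudy no margin, matching scale, decision rule or composite outcome, so the protocol's non-inferiority aim is not addressed

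*SAP*

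**What the plan says.** **Protocol.** Section 11.2.1 gives the DAPT substudy a non-inferiority aim; the "corresponding null hypothesis is that short duration of treatment is inferior than standard duration on this outcome". Section 11.2.4 makes the primary outcome a composite: "new stroke event (ischaemic or haemorrhagic) over 12 months". Section 11.2.6 states that "a relative non-inferiority margin of 40% (i.e. risk ratio 1.4) was used" and that "A sample size of 2366 provides 90% power (1-sided $\alpha = 0.025$) to reject a non-inferiority margin of 1.4". Its inputs are a 10% risk on standard duration and equal true risks. The same section calls this calculation preliminary and says the substudy will take as many patients as it can to inform a later trial. Section 10.2 leaves the details of all analyses to the SAP.

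**SAP.** Section 3.9 is one short text for both substudies. It opens by giving feasibility of later confirmatory trials as their main purpose, with recruitment, safety and adherence as the things to be learned. It then lists ischaemic recurrence, ICH, death and SAEs as separate 12-month outcomes, and says: "The effect of the intervention will be estimated using the same approach as in the binary analysis of mRS (see Section 3.8.1"). Section 3.8.1 is a random-effect logistic regression reported as an odds ratio with a 95% CI. Neither section mentions non-inferiority, a margin, a one-sided alpha or a rule for reaching a conclusion.

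**The concern.** The two substudies ask different kinds of question. The anticoagulation substudy (Protocol 11.1.1) has a superiority aim, for which an odds ratio and its interval around 1 is a natural summary. The DAPT substudy does not: its null is that short duration is worse, and that null can be rejected only against a stated margin. Four things needed for that are absent from SAP 3.9:

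- the margin;
- an estimate on the margin's scale (the margin is a risk ratio, the output an odds ratio);
- a rule linking the interval to a conclusion;
- the composite outcome to which the margin applies.

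Without them, someone reporting the substudy has an odds ratio, an interval and, most likely, a non-significant difference. In a small sample that result is expected whether or not short duration is acceptable. The risk is that it gets reported as showing the two durations to be equally effective.

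**Working it through.** **Inputs.** Standard-arm risk 10%, no true difference, risk-ratio margin 1.4, one-sided alpha 0.025, 90% power and total 2366 (Protocol 11.2.6); 1:1 allocation (Protocol 11.2.3). The substudy sizes of 300, 500 and 900 are assumptions, since the documents give no expected pilot size. All figures are normal approximations that ignore site effects and covariates; m is the number per arm.

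**1. Reproducing 2366.** At a 10% risk, a ratio of 1.4 means 14%, a difference of 0.04.

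m = (1.960 + 1.282)² × 2 × 0.10 × 0.90 / 0.04² = 1182.1, rounded up to 1183, so 2366 in total.

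This is an exact match. The stated 90% power therefore belongs to a 4-point risk-difference margin with no dropout allowance.

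**2. The same N on other scales** (m = 1183, equal risks of 10%):

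- Log risk ratio: SE = √(2 × 0.90 / (0.10 × 1183)) = 0.1234. Power = Φ(ln 1.4 / 0.1234 − 1.960) = Φ(0.768) = 78%.
- Log odds ratio: the equivalent margin is (0.14/0.86) / (0.10/0.90) = 1.465. SE = √(2 / (0.09 × 1183)) = 0.1371. Power = Φ(0.3819 / 0.1371 − 1.960) = 80%.

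So the planned odds-ratio interval cannot be set directly against 1.4, and neither ratio scale carries the stated 90%.

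**3. How often p > 0.05 when short duration is exactly at the margin** (10% versus 14%).

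SE = √((0.10 × 0.90 + 0.14 × 0.86) / m) = √(0.2104 / m), and P(p > 0.05) ≈ Φ(1.960 − 0.04 / SE).

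| Total N | m | SE | 0.04/SE | P(p > 0.05) |
|---|---|---|---|---|
| 300 | 150 | 0.0375 | 1.07 | 81% |
| 500 | 250 | 0.0290 | 1.38 | 72% |
| 900 | 450 | 0.0216 | 1.85 | 54% |
| 2366 | 1183 | 0.0133 | 3.00 | 15% |

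A correct comparison with the margin would wrongly declare non-inferiority in about 2.5% of such trials.

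**4. What a correct comparison delivers when the durations are truly equal.** The formula in step 2, on the log risk-ratio scale, gives 16%, 24% and 39% at 300, 500 and 900.

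**5. An illustration at 500 patients.** With 30/250 events on short and 25/250 on standard duration, the odds ratio is 1.23 (0.70 to 2.15), p = 0.48. The risk ratio is 1.20 (0.73 to 1.98). The difference is not significant, yet the upper limit is far above 1.4, so non-inferiority is not shown.

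**The case against.** The strongest reply is that SAP 3.9 plans estimation, not a test. It says the effect will be estimated, 3.8.1 reports an interval, and a two-sided 95% CI is the usual tool for a one-sided 0.025 non-inferiority reading. The p-value columns in SAP Tables 13 and 14 are for the main trial, and there are no substudy table shells. The substudy is also a pilot in both documents, and the 1.4 margin appears only in a calculation labelled preliminary.

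Much of this stands. A reader might infer that the SAP tests superiority against an odds ratio of 1, and that a non-significant p-value is then the only output bearing on the aim. The documents do not say so: no null is named for the substudies, and an interval is promised. A reader might also set the 5% rejection rate of such a test under equality against the 78% in step 2 and call the gap lost power. That compares the type I error of one hypothesis with the power of another. It also uses a size the substudy cannot reach, since its patients come from a parent trial of 2257 and only those with large artery atherosclerosis qualify.

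What does not stand is the idea that an interval alone is enough. It can be read for non-inferiority only if margin, scale, outcome and rule are fixed beforehand, and SAP 3.9 fixes none of them. Nor does pilot status remove the mismatch: the protocol's non-inferiority null remains, the SAP still commits to a comparative estimate, and neither says whether the hypothesis is addressed or set aside.

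**Conclusion.** The concern holds as a mismatch between protocol and SAP. The protocol sets a non-inferiority aim with a risk-ratio margin and a composite outcome; SAP 3.9 provides an odds ratio on separate outcomes with no margin or rule. The logistic model itself is not the fault.

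The consequence is a risk of misreading, largest in small samples: at a true risk ratio of 1.4, p > 0.05 in about 81%, 72% and 54% of trials of 300, 500 and 900. These figures rest on the protocol's 10% event rate, the assumed sizes, and a reader who treats non-significance as reassurance; the SAP does not itself prescribe that reading. Because the substudy is a pilot, this should be corrected, but it does not undermine a confirmatory result or touch the main trial.

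**What to change.** In SAP 3.9, give the DAPT substudy its own text:

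- Analyse the protocol's composite of new ischaemic or haemorrhagic stroke over 12 months, with the separate outcomes kept as supporting.
- From the same logistic model, derive by marginal standardisation the risk ratio (short versus standard) with a two-sided 95% CI.
- Compare the upper limit with 1.4. Report non-inferiority as 'not established' unless the limit is below 1.4.
- State that p > 0.05 against an odds ratio of 1 is not evidence of non-inferiority.
- State that the comparison is exploratory because the substudy is a pilot.
- Record that 2366 with 90% power corresponds to a 4-point risk-difference margin, and that power at that size is about 78% on the log risk-ratio scale.

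The cost is a short paragraph, one composite variable built from events already planned for collection, and one derived estimate. The downside is that a pilot-sized sample will probably report 'not established': even with truly equal durations, the rule is met in only about 16% to 39% of trials at 300 to 900 patients.
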